The wingless (Wnt) signalling protein family is essential for embryogenesis and adult tissue homeostasis. It is emerging that Wnt signalling is a driving force in many disease states including atherosclerosis. Wnt signalling can promote an inflammatory response in monocytes/macrophages (a type of white blood cell) and causes dysfunction of endothelial cells (a type of cell that lines the inner walls of arteries)-keys steps in the development of atherosclerosis. (Blankesteijn *et al.* 2015) Some studies in lung cancer cells and heart muscle cells have shown that IGFBP6 can inhibit the Wnt signalling pathway, illustrating an important interaction between the IGF and Wnt families. (Bach 2016)

Preliminary data from our laboratory studies has established that monocytes from the blood of people with periodontal disease had reduced levels of IGFBP-6 and this reduction can enhance invasion of monocytes into coronary arteries- a key stage in atherosclerosis. Furthermore, we looked at proteins that can be influenced by IGFBP-6 and saw significantly enhanced levels of Egr1 in monocytes from people with periodontal disease compared to the levels detected in healthy controls. Egr1 is a protein that can be activated as a result of infection and plays a role in the pathophysiology of atherosclerosis (Blaschke *et al.*2004).

We have also identified that Wnt proteins in patients with periodontal disease are enhanced compared to controls. A preliminary analysis demonstrated that NOTUM, an antagonist of Wnt signalling, was decreased in both the plasma and monocytes from patients with periodontal disease. These changes in Wnt signalling may promote atherosclerosis in people with periodontal disease.

The main benefit of this research will be a fuller understanding of the pathogenesis between periodontitis and atherosclerosis, and in the longer-term, the identification of new treatments and biomarkers, for better diagnosis, management, and life quality for patients. The findings will be transferrable to other inflammatory conditions, such as stroke, diabetes mellitus, and rheumatoid arthritis.

Study Aim & Objectives

Aim:

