Clinicians or a member of the dental team at the University of Bristol Dental School will approach participants who are attending the hospital for either periodontal assessment or regular dental appointments (healthy volunteers).

- Potential donors will be provided with the same participant information leaflet (see enclosed) containing information about the research. Sufficient time will be provided to participants prior to
- Written consent will be obtained from participants to allow for a basic periodontal examination, and collection of a blood sample. Every 5th person will be asked to provide a sample of saliva.

Inclusion/exclusion criteria for people with periodontitis

Inclusion:

- All people over the age of eighteen (18)
- Capacity to consent
- Attending a scheduled dental appointment at the University of Bristol Dental Hospital
- People with unstable severe periodontitis or a high susceptibility to periodontitis (as defined by the British Society of Periodontology 2019 implementation of the 2017 World Workshop Classification of periodontal and peri-implant diseases and conditions: Stage III/IV and Grade C.)
- At least 18 erupted teeth

Exclusion

- All people under the age of eighteen (18)
- Those who lack capacity to consent
- History of cardiovascular disease such as hypertension, angina, previous myocardial infarction, heart failure, aortic disease, arrhythmia, heart valve disease.
- History of autoimmune/autoinflammatory diseases such as Sjogren's syndrome,
 - rheumatoid arthritis, inflammatory bowel disease, systemic lupus erythematosus, or systemic sclerosis
- History of endocrine disease including diabetes mellitus types 1 and 2
- Currently taking antibiotics or has had antibiotics in the preceding 6 months
- People taking statins, non-steroidal anti-inflammatory medications, immunosuppressive medications or corticosteroids.
- Smokers of tobacco (including Vaping/e-cigarettes)
- History of salivary gland disease or oral mucosa disease

Inclusion/exclusion criteria for healthy volunteers

Inclusion:

- All people over the age of eighteen (18)
- Capacity to consent
- Attending a scheduled dental appointment
- People with no evidence of periodontitis
- At least 18 erupted teeth

Exclusion

- All people under the age of eighteen (18)
- Those who lack capacity to consent
- History of cardiovascular disease such as hypertension, angina, previous myocardial infarction, heart failure, aortic disease, arrhythmia, heart valve disease

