- History of autoimmune/autoinflammatory diseases such as Sjogren's syndrome,
 rheumatoid arthritis, inflammatory bowel disease, systemic lupus erythematosus, or
 systemic sclerosis
- History of endocrine disease including diabetes mellitus types 1 and 2
- Currently taking antibiotics or has had antibiotics in the preceding 6 months
- People taking statins, non-steroidal anti-inflammatory medications, immunosuppressive medications or corticosteroids.
- Smokers of tobacco (including Vaping/e-cigarettes)
- History of salivary gland disease or oral mucosa disease

Ethical Considerations and information

Blood and saliva samples will be collected from participants who are capable of informed decision making. Treating clinicians or an appropriately qualified member of their team will obtain informed consent from participants. In general terms, participants will be asked to provide a sample of blood and saliva that will be used in this study to better understand the link between periodontal disease and atherosclerosis. Participant information leaflets and consent forms will be provided (see enclosed).

Sample Collection

Objective 1 and 2b

Upon obtaining consent, the clinical practitioner will collect two tubes of peripheral blood (approximately 20mls in total) from the forearm of the person using standard venepuncture techniques.

The clinical practitioner will ask every 5th person to provide a saliva sample. Whole saliva will be collected in polypropylene vials using the passive drool method (2mls in total). The person will undergo a basic periodontal screen to assess gum health using the previously validated 'Basic Periodontal Exam' (BPE)/ 'Periodontal Probing Depth', as well as recording if there is 'bleeding on probing'. (Dietrich *et al.* 2019). The exam and collection of samples will occur before dental treatment begins. After blood and saliva has been collected, and the periodontal screen performed, the person will have no further participation in the study.

Objective 2a

Upon obtaining consent, the clinical practitioner will collect two tubes of peripheral blood (approximately 20mls in total) from the forearm of the person using standard venepuncture techniques, and saliva will be collected (2mls in total).

The person will undergo a basic periodontal screen to assess gum health using the previously validated 'Basic Periodontal Exam' (BPE)/ 'Periodontal Probing Depth' as well as recording if there is 'bleeding on probing'. (Dietrich *et al.* 2019)

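### Neither exclusion list names current acute infection or untreated non-periodontal dental infection, so people with either may enter both groups and confound the case-control comparison

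*Protocol*

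**What the plan says.** The exclusion lists for patients and for healthy volunteers (Protocol, inclusion/exclusion criteria) have the same content. Besides age and capacity, they cover chronic cardiovascular, autoimmune and endocrine disease and smoking or vaping. Three further items come near infection:

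- "Currently taking antibiotics or has had antibiotics in the preceding 6 months"
- "People taking statins, non-steroidal anti-inflammatory medications, immunosuppressive medications or corticosteroids"
- "History of salivary gland disease or oral mucosa disease"

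Under Participants and recruitment, people are approached when "attending the hospital for either periodontal assessment or regular dental appointments (healthy volunteers". The oral-health requirements for a control are "People with no evidence of periodontitis" and at least 18 erupted teeth.

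Under Sample Collection, "The person will undergo a basic periodontal screen to assess gum health", using the basic periodontal examination or probing depth, with bleeding on probing recorded. For Objectives 1 and 2b, "The exam and collection of samples will occur before dental treatment begins", and these participants then leave the study.

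The background reports raised Egr1 in patients' monocytes and adds that "Egr1 is a protein that can be activated as a result of infection". The macrophage outcomes in Objective 1 include iNOS, IL-6, arginase and IL-10. The Analysis section names t-tests and ANOVA and mentions no covariate.

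**The concern.** The lists set out to remove inflammatory states other than periodontitis, but leave current infection unnamed. The antibiotic item identifies people whose infection was treated. An infection that has not been treated with antibiotics passes it.

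An infected control may have monocyte or inflammatory-marker values closer to those of a patient, which would shrink the contrast. A patient with an additional infection may show a difference that is not due to periodontitis, which would widen it. The two groups come from different types of appointment, so the two errors need not cancel.

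The problem would be hard to repair later. The protocol describes no record of infection status, the researchers do not hold the link between code and person, and participants in Objectives 1 and 2b are not seen again for the study. An analysis plan could adjust for infection only if it had been recorded at sampling.

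**Working it through.** **Step 1: the criteria set against the gap.** No stated figure bears on this point, so the main check is a reading of both lists.

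| Protocol element | What it removes or detects | What remains eligible or unseen |
|---|---|---|
| Antibiotics now or within 6 months | Infection treated with antibiotics | Infection not so treated |
| NSAID, corticosteroid, immunosuppressant or statin use | Some people with symptoms, through their medication | Infected people not taking these drugs |
| Salivary gland or oral mucosa disease | Disease of those tissues | Pulpal or periapical infection, abscess |
| Controls: no evidence of periodontitis, at least 18 teeth | Periodontitis | Tooth infection of other origin |
| Periodontal screen | Gum status | Not aimed at tooth infection |
| Sampling before dental treatment (Objectives 1 and 2b) | Nothing | An existing dental infection is still untreated at the draw |

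No element names acute infection, febrile illness or untreated dental infection. The gap is therefore present in both lists.

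**Step 2: scale, as an illustration only.** Inputs from the Sample size determination section for Objective 1: n = 125 per group, power 90%, a change of 50%, and p<0.005. Two-sided testing is assumed. No standard deviation is given, so the stated sample size cannot be reproduced independently. The standard deviation is instead solved from it:

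SD = difference / [(z for alpha + z for power) × √(2/n)]
= 50 / [(2.807 + 1.282) × √(2/125)]
= 50 / (4.089 × 0.1265)
= 96.7% of the mean, so d = 50/96.7 = 0.517.

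Let f be the share of controls infected and s the fraction of the patient-control difference that an infected control takes on. Neither is in the documents. Then

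remaining difference = 50 × (1 − f × s)
power = Φ[4.089 × (1 − f × s) − 2.807]

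| f | s = 1: difference, power | s = 0.5: difference, power |
|---|---|---|
| 0 | 50%, 90% | 50%, 90% |
| 5% | 47.5%, 86% | 48.75%, 88% |
| 10% | 45%, 81% | 47.5%, 86% |
| 20% | 40%, 68% | 45%, 81% |

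With the full shift, restoring 90% power would take 139, 155 and 196 per group at 5%, 10% and 20% infected.

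**Step 3: sensitivity to alpha.** At alpha 0.05 the solved SD is 121.9% of the mean (d = 0.410). The full-shift powers become 87%, 83% and 74%, so the pattern does not depend on the unusually small alpha.

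**Step 4: the other direction.** The table places infection in controls only. Additional infection among patients could push the difference up. Without the shares in each group, the sign of the net error is unknown.

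**The case against.** The strongest reply is that the plan already makes infection unlikely. Controls come for regular, scheduled visits, and the antibiotic, NSAID and corticosteroid items remove some people with symptomatic or recently treated infection. This stands as a reason to expect a small share. It does not close the gap, because each item works through treatment and not through infection itself.

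Second, the power losses rest on assumed shares and, in the worst column, on every infected control reaching the level of patients with severe disease. That is fair, and it is why the half shift is shown beside it. The figures also concern only the patient-control contrast in blood. Experiments A to F each include a treated-versus-untreated contrast within one group, and between-group dilution does not apply there. Objective 2b is sized on saliva, and the documents do not link infection to salivary levels.

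Third, a reader might infer that the protocol itself says infection activates the pathway under study. It does not. The statement is made of Egr1 alone, and only as something that can happen. Egr1 is described as influenced by IGFBP-6 and is not a named outcome. The text on Wnt says that Wnt signalling can promote inflammation, not that infection alters Wnt signalling or IGFBP-6. The case for concern rests more on the inflammatory markers among the outcomes.

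Fourth, for patients, periodontal infection belongs to the condition studied. Only infection beyond it confounds.

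**Conclusion.** The point holds as a gap in the eligibility criteria that is worth closing. Current acute infection and untreated non-periodontal dental infection are caught only indirectly, so such people may enter either group and confound the comparison of monocyte, inflammatory-marker and biomarker levels.

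The documents do not support the stronger inference that infected people will in fact serve as controls and cases: they give no prevalence, and several criteria reduce the likelihood. Nor do they fix the direction or size of the error. The illustrative fall for Objective 1, from 90% power to between 88% and 68% across the assumed shares and shifts, shows only that the matter could be more than trivial.

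It would also be wrong to say that one blood draw represents every participant. Patients in Objective 2a are sampled before and after treatment. There the risk takes another form: if routine dental treatment also cleared a coexisting tooth infection, that change could be read as a response to periodontal treatment.

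**What to change.** Add one line to both exclusion lists: current acute infection or febrile illness, or known untreated dental infection other than periodontitis. Apply it before sampling, in the same way in both groups, through a history question and the findings the dental team already has. The periodontal screen should not be relied on for this, since it is not aimed at tooth infection.

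Where possible, defer sampling to a later scheduled appointment so that the participant is not lost.

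Record infection status with the sample code. If an infection comes to light after sampling, keep the participant in the main comparison and address the matter in a sensitivity analysis. Patients under treatment may be examined more often than controls, so removing people after sampling could itself differ by group.

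The cost is one line per list, one question and one recorded item. The downside is that a few donors are deferred or replaced, and an infection that is neither known nor reported will still be missed.

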В	Control + IgG control	Control + BP6 Nab	Periodontitis + IgG control	Does neutralizing IGFBP6 in control cells mimic effects observed in cells from periodontal patients?
С	Control + vehicle	Periodontitis + vehicle	Periodontitis + BP6	Does addition of IGFBP6 to cells from periodontal patients mimic control cells?
D	Control + vehicle	Periodontitis + vehicle	Periodontitis + ETC-159	Does inhibition of Wnt secretion (using ETC-159) in cells from periodontal patients mimic control cells?
E	Control + vehicle	Periodontitis + vehicle	Periodontitis + iCRT	Does inhibition of Wnt/b-catenin signalling (using iCRT) in cells from periodontal patients mimic control cells?
F	Control + vehicle	Control + 400ng/ml Wnt3a	Periodontitis + vehicle	Does treatment of control cells with Wnt3a mimic cell from periodontal patients?

Table I: summary of the design of in vitro experiments

2. Assessing the potential use of IGFBP6 and Wnt proteins as suitable biomarkers

a) Peripheral blood and saliva will be collected from patients with periodontal disease both pre and post treatment and age and gender matched healthy controls. b) Saliva samples will be collected from people with severe periodontitis and age and gender matched controls.

The seven Wnt proteins and IGFBP6 identified by our previous proteomic analysis will be quantified in plasma, isolated monocytes and saliva, and the levels in patients and controls statistically compared. Standard laboratory techniques including western blot and specific enzyme-linked immunosorbent assays (Bio-Plex, Bio-Rad Laboratories Ltd. Hertfordshire, UK) will be used to assess for changes.

This will determine whether IGFBP6 and/or any of the seven Wnt pathway proteins are associated with periodontitis and could lead to future work investigating the role of these proteins in disease progression. Is it likely that other novel findings will be identified and scope to explore these will be undertaken under the current protocol.

See protocols 1-3.

Study sites

 University Hospitals Bristol and Weston NHS Foundation Trust ,[name]

Translational Health Sciences, Research Floor, Level 7, University of Bristol, Bristol Royal Infirmary, [name] (location of laboratory and storage location for samples)

Participants and recruitment

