The person will then undertake their routine dental treatment. The time it takes for the successful completion of dental treatment varies, as do the number of necessary appointments, but typically it can take approximately 24 weeks. On completion of this dental treatment the person will be asked to provide one additional peripheral blood sample (approximately 20mls) and saliva (2mls in total) sample. After this second sample of blood and saliva has been collected these participants will have no further participation in the study.

For all the objectives listed above, the clinical practitioner will then anonymise all samples by allocating a code to the samples. Only the clinical practitioners will have access to the code that links the samples and people, not the researchers. Once anonymised, samples will be made available to the researchers, who will analyse the samples using established laboratory techniques as mentioned above.

Duration of participant involvement

Objectives 1 and 2b: participants will be actively involved in the study for approximately 20 minutes at their assessment appointment.

Objective 2a: from the time of their assessment appointment to the successful completion of their dental treatment, the participants will have taken part in the study for approximately 24 weeks. The total amount of time the participant will be actively involved in the study will be approximately 35 minutes, spread over the two appointments.

Sample size determination

From our previous data with similar experimental design and analyses, we have calculated the sample size (**power analysis**) using an online sample size calculator (https://clincalc.com/stats/samplesize.aspx) and p<0.005

Objective 1: Mechanism of regulation

Approximately 150 gum disease (severe periodontitis) participants and 150 control participants (good gum health) will be approached. From these approaches we hope to obtain samples of blood from 125 severe periodontitis and 125 control participants. The sample size is based on previously published studies and our own previous work, and shown to provide a 90% power to detect a 50% change. (Willi *et al.* 2014; Nanbara *et al.* 2012)

Objective 2: Biomarker potential

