a) Approximately 20 gum disease (severe periodontitis) participants and 20 control participants (good gum health) will be approached. From these approaches we hope to obtain samples of blood and saliva from 12 severe periodontitis and 12 control participant The sample size is required to provide >90% power to detect a 30% change in protein expression.

b) Approximately 30 gum disease (severe periodontitis) participants and 30 control participants (good gum health) will be approached. From these approaches we hope to obtain saliva samples from 20 people with severe periodontitis and 20 control participants
 The sample size is required to provide a 80% power to detect a 20% change. (Jasim *et al.* 2018)

Analysis

Data will be analysed by t-tests when two groups are compared or by ANOVA if more than two groups are assessed.

Withdrawal of participants

Participants will be informed that they can withdraw from the study at any stage- no reason needs to be provided. Withdrawal from the study will not affect their dental care.

Any blood and saliva donated by a participant is a gift, and any samples or data collected up until the point the participant wants to withdraw will be kept, used and included in analysis.

Safety and adverse events

There is minimum risk to taking blood from participants. All clinical study procedures will be carried out on clinics at Bristol Dental Hospital by appropriately trained staff. All cross infection controls will be implemented including those related to COVID 19. All study material is participant specific and all clinical study staff are trained in Good Clinical Practice (GCP). All procedures are performed by clinical staff that have appropriate qualifications and training.

A slight discomfort and bruising may be experienced due to withdrawal of blood. There should be no major adverse effects, pain, discomfort, distress, intrusion, inconvenience or changes to lifestyle as this is a routine blood donation of small volume. No adverse effects are associated with collecting saliva.

Any adverse events should be reported to [name] who will review, record and if necessary, report all events to the UHBW R&I office via the University Hospitals Bristol and Weston adverse event reporting system (UHBW undertake this role on behalf of the Sponsor).

Data management

Confidentiality:

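### Objective 2b promises age and gender matched controls, but the every-5th-person saliva rule that picks its participants does not select them; the 2a baseline saliva could also be analysed with it

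*Protocol*

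**What the plan says.** Under the study objectives, item 2(b) sets the comparison: "Saliva samples will be collected from people with severe periodontitis and age and gender matched controls". Item 2(a) also specifies age and gender matched healthy controls. Objective 1 speaks only of healthy controls and states no matching.

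How people are chosen to give saliva appears in two places. Participants and recruitment says, straight after the sentence on written consent: "Every 5th person will be asked to provide a sample of saliva". Sample Collection, under the joint heading for Objectives 1 and 2b, opens with "Upon obtaining consent, the clinical practitioner will collect two tubes of peripheral blood" and then says: "The clinical practitioner will ask every 5th person to provide a saliva sample". Neither place says whether the count runs within each group or over both, and neither refers to age, gender or a paired case.

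Sample size determination gives, for Objective 1, "Approximately 150 gum disease (severe periodontitis) participants and 150 control participants (good gum health) will be approached" and "From these approaches we hope to obtain samples of blood from 125 severe periodontitis and 125 control participants". For Objective 2b it gives "Approximately 30 gum disease (severe periodontitis) participants and 30 control participants (good gum health) will be approached", with 20 saliva samples hoped for per group and 80% power for a 20% change. Objective 2a is sized separately at 12 per group, with blood and saliva. The significance level given is p<0.005. The Analysis section names t-tests for two groups and ANOVA for more than two.

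**The concern.** A matched design needs a step that chooses controls by reference to the cases. Here the selection step for 2b is a systematic 1-in-5 pick from people attending, and nothing ties that pick to a case's age or gender. The pick can be no better balanced than the stream it is drawn from, and the stream is the Objective 1 one, where no matching is stated. The named analysis, a plain t-test, would not correct any imbalance. A difference in salivary protein between groups could then partly reflect age or gender, which is what the promised matching is meant to prevent.

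Timing matters too. Under Sample Collection, participation in Objectives 1 and 2b ends once samples are taken and the periodontal screen is done, so a control who was not asked for saliva at that visit cannot be added later under the protocol.

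A second, smaller point is a missed gain. Objective 2a will hold baseline saliva from 12 + 12 people who meet the same eligibility criteria, measured for the same seven Wnt proteins and IGFBP6. The protocol does not say whether this material joins the 2b case-control comparison.

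**Working it through.** **1. The plan's own counts.** Inputs per group: 150 approached and 125 giving blood (Objective 1); 30 approached and 20 saliva samples (Objective 2b); a 1-in-5 rule applied after consent.

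- Approached: 150 / 5 = 30, which reproduces the stated figure.
- Consented and asked: 125 / 5 = 25, which equals 30 × 125/150.
- Obtained: 20, so the implied uptake among those asked is 20/25 = 80%.
- Chance of at least 20 samples from 25 asked at 80% uptake (binomial): 62%. For comparison, at least 20 from 30 at 20/30 = 67%: 58%.

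The protocol does not spell out this chain, but its figures fit it. The numbers are not the problem.

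**2. What the rule does to matching.** Three cases cover the possible readings:

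- *Controls in the Objective 1 stream are not matched* (nothing says they are). A 1-in-5 pick reproduces whatever age and gender differences that stream has.
- *Controls are frequency matched at recruitment* (not stated). The pick keeps that balance in expectation.
- *Controls are individually paired and each group is counted separately* (not stated). A selected case's partner is selected about 1 time in 5, so of 25 cases asked about 25 × 1/5 = 5 would have their own control asked.

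Only the second reading gives a matched comparison, and the protocol does not set it up.

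**3. What the rule does to group sizes.** If the count runs over both groups, 250 / 5 = 50 people are asked. With attendance in random order (an assumption), the number from one group is hypergeometric with mean 25 and SD = √(50 × 0.5 × 0.5 × 200/249) = 3.17.

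- 95% range for one group: about 19 to 31.
- Chance that one of the groups has fewer than 20 people asked: about 8%.
- At 80% uptake, a 19/31 split would give about 19 × 0.8 = 15 and 31 × 0.8 = 25 samples.

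If the count runs within each group, both are 25 and this does not arise.

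**4. Gain from the 2a baseline saliva.** Pooled size: 20 + 12 = 32 per group. No SD is given, so the standardised effect d is solved from the stated 80% power at 20 per group (two-sided two-sample t-test, noncentral t). The implied coefficient of variation (CV) is 0.20 / d.

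| Two-sided alpha | d implied | CV implied | Power at 20 | Power at 32 |
|---|---|---|---|---|
| 0.005 | 1.217 | 0.164 | 80% | 97% |
| 0.05 | 0.909 | 0.220 | 80% | 95% |

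A normal approximation gives nearly the same: d = (2.807 + 0.842) × √(2/20) = 1.154 at 0.005, and power at 32 = Φ(1.154 × √16 − 2.807) = Φ(1.808) = 96%. At 0.05 it gives 94%.

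**The case against.** The best defence on matching is that the protocol nowhere sets up individual pairs. A 1-in-5 pick is unrelated to age and gender, so if the two groups are balanced at recruitment the subsample stays balanced on average. That is right as far as it goes, and it is why one should not say that the rule breaks the matching. But it needs a matching step in the Objective 1 stream, and the protocol states none. The gap between the promise in 2(b) and the stated rule remains.

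The best defence on pooling is that 2a is a separate objective with its own sizing. Sizing 2b without it is conservative, and joint analysis may be settled in an analysis plan that is not at hand. This also stands. Pooling is an improvement on offer, not the repair of an error.

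A reader might infer something stronger: that 25 people asked, at an uptake of 20/30, yield 25 × 20/30 = 16.7, or about 17 per group, so that 2b misses its 80% power. The protocol does not support this. Its 20 of 30 is a yield from people *approached*, so it already includes refusals of consent. Applying it to 25 people who have consented counts those refusals twice. No 67% uptake among consenters is stated anywhere, and 80% uptake gives exactly 20. A reader might also treat 2b as a separate group of 30, of whom the rule would ask only 6. The shared procedure heading and 150 / 5 = 30 point instead to 2b being nested within Objective 1.

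**Conclusion.** The point holds in limited form. The protocol promises age and gender matched controls for 2b, and the rule that selects 2b participants does not provide them. How much bias follows cannot be sized, because the protocol gives no age or gender distribution for either stream. Equal group numbers are assured only if the count runs within each group, which is not stated. Counted over both groups, the split could be about 19 to 31 of 50, on the assumption of random attendance order.

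Using the 2a baseline saliva would raise power for the 20% change from the stated 80% to about 97% at p<0.005, or 95% at p<0.05. This rests on the SD implied by the plan's own 80% claim, which cannot be checked independently. It also assumes that the 20 samples per group in 2b and the 12 per group in 2a are obtained from different people.

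The documents do not show a shortfall in 2b's sample size or power, and the 1-in-5 fraction needs no change.

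**What to change.** 1. In Participants and recruitment and in Sample Collection, state that the every-5th count runs within the periodontitis group. For controls, replace the count with selection by match: ask for saliva from consenting controls chosen to match the selected cases on age and gender, either individually or by frequency, and say which. The cost is some wording and a little clinic effort, since controls are chosen by match and not by order of attendance. No extra participants are needed.

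2. In Sample size determination, show the chain of 30 approached, 25 asked and 20 obtained per group, so that the base of the rule is plain.

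3. State that the saliva case-control comparison uses the pre-treatment 2a samples (12 + 12) together with the 2b samples (20 + 20), in a model with a term for objective and each person counted once. Use the 2a post-treatment saliva only for the pre/post contrast. This costs no further collection, only analysis wording.
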